6.9 Behavioral and Counseling Evaluations

Eligibility behavioral assessments conducted at the Screening Visit will assess a woman's alcohol and drug use to determine whether related inclusion/exclusion criteria are met.

Site staff will counsel enrolled women about the signs and symptoms of active TB at the enrollment visit and each study follow-up visit. Women will be asked to come to the clinic for an interim visit should any of the symptoms develop during the course of the study.

HIV pre-/post-test counseling will be offered per local standard of care in the event that HIV testing must be performed by the site in order to confirm HIV status. Participants requiring HIV testing and counseling during study participation will be referred to local providers.

6.10 Procedures for Premature Discontinuation of Study Drug Regimen/Study Participation

Women who permanently discontinue the study drug regimen (i.e., RPT, INH, and pyridoxine) prematurely will remain on-study and follow the visit schedule until 24 weeks postpartum. Infants of mothers who permanently discontinue study drug regimen will also remain on study per the visit schedule until 24 weeks of life.

Participants who must be withdrawn from study participation will be requested to complete their Study Exit Visit, if possible.

7 SAFETY MONITORING, ASSESSMENT AND REPORTING

An adverse event (AE) is defined as any untoward medical occurrence in a clinical research participant administered an investigational product and which does not necessarily have a causal relationship with the investigational product. As such, an AE can be an unfavorable or unintended sign (including an abnormal laboratory finding, for example), symptom or disease temporally associated with the use of an

investigational product, whether or not considered related to the product. This definition is applied at the time of enrollment (i.e., once a participant has successfully completed the SES). The term “investigational product” for this study refers to the study drug regimen.

Women will be provided instructions for contacting the study site to report any untoward medical occurrences they or their infants enrolled in the study may experience. In cases of potentially life-threatening events, participants will be instructed to seek immediate emergency care. Where feasible and medically appropriate, participants will be encouraged to seek evaluation at the hospital/clinic where a study clinician is based, and to request that the clinician be contacted upon their arrival.

7.1 Safety-Related Roles and Responsibilities

Routine monitoring will be done by the IMPAACT 2001 Core Team which consists of the Protocol Chair, Vice Chairs, NIAID and NICHD Medical Officers, Protocol Statisticians, Protocol Data Manager, and the Clinical Trials Specialist ([contact]) or their designees. Site IoRs/designees are responsible for continuous close safety monitoring of all study participants, and for alerting the Core Team if unexpected concerns arise. The IMPAACT SDMC prepares routine safety monitoring and clinical data reports for review by the Core Team, which meets via conference call approximately twice per month or as needed throughout the period of study implementation to review safety data, discuss product use management, and address any potential safety concerns.

An IMPAACT Study Monitoring Committee (SMC) will review the study regularly, at least twice annually, and on a more frequent or ad hoc basis for safety issues or any other concerns. Other study implementation issues, such as participant accrual, participant retention, and data quality, will also be monitored by the SMC. The protocol team may also request ad hoc SMC reviews if any potential safety concerns arise. For example, if a potential concern is identified during a routine protocol team review of safety data, the team may request an ad hoc SMC review to further evaluate that potential concern. Based on any of its reviews, the SMC may recommend that the study proceed as currently designed, proceed with design modifications, or be discontinued.

7.2 Safety-Related Recording on Case Report Forms

Study site staff will document in source documents all AEs reported by or observed in enrolled study participants regardless of severity and presumed relationship to study product.

Pre-existing conditions and AEs identified in this study will be recorded on CRFs as abnormal laboratory test results, signs, symptoms, and diagnoses, as follows:

Laboratory test results: The results of all protocol-specified screening, entry, and follow-up laboratory test results will be recorded on the relevant CRFs. In addition, throughout follow-up through the Study Exit Visit, Grade 2 or higher test results related to pregnancy complications, hepatotoxicity, hemorrhage, or peripheral neuropathy, all Grade 3 or higher test results, test results that result in discontinuation of study drug regimen, and test results that meet criteria for EAE reporting (included congenital anomalies) will be further evaluated, with additional data recorded on the relevant event evaluation CRF.

Signs and symptoms: All signs and symptoms occurring from the Screening Visit through immediately prior to the first administration of study drug regimen will be recorded as pre-existing conditions on the relevant CRF. While maternal participants are receiving study drug, all signs and symptoms will be recorded on the relevant CRF. Thereafter, Grade 2 or higher signs and symptoms related to pregnancy complications, hepatotoxicity, hemorrhage, or peripheral neuropathy, all Grade 3 or higher signs and symptoms, and signs and symptoms that meet EAE reporting criteria will be recorded on CRFs. In addition, throughout follow-up through the Study Exit Visit, Grade 3 or higher signs and symptoms, signs and symptoms that result in discontinuation of study drug regimen and signs and symptoms that meet

criteria for EAE reporting (included congenital anomalies) will be further evaluated, with additional data recorded on the relevant event evaluation CRF.

Diagnoses: All diagnoses identified from the Screening Visit through immediately prior to the first administration of study drug regimen, except Grade 1 and Grade 2 diagnoses listed on the IMPAACT Do Not Record list (available at www.fstrf.org), will be recorded as pre-existing conditions on the relevant CRF. During follow-up through the Study Exit Visit, all diagnoses since the last study visit except Grade 1 and Grade 2 diagnoses listed on the IMPAACT Do Not Record list will be recorded on the relevant CRF. In addition, throughout follow-up, Grade 2 or higher diagnoses related to pregnancy complications, hepatotoxicity, hemorrhage, or peripheral neuropathy, all Grade 3 or higher diagnoses, diagnoses that result in discontinuation of study drug regimen, and diagnoses that meet criteria for EAE reporting (including congenital anomalies) will be further evaluated, with additional data recorded on the relevant event evaluation CRF. All diagnoses recorded on CRFs should be recorded consistent with the specifications of the relevant diagnosis appendix (available at www.fstrf.org).

With appropriate permission of the participant/mother, whenever possible, records from all non-study medical providers related to untoward medical occurrences will be obtained and required data elements will be recorded on study CRFs.

7.3 Expedited Adverse Event (EAE) Reporting

7.3.1 Adverse Event Reporting to DAIDS

Requirements, definitions and methods for expedited reporting of adverse events (AEs) are outlined in Version 2.0 of the DAIDS EAE Manual, which is available on the RSC website at <http://rsc.tech-res.com/safetyandpharmacovigilance>.

The DAIDS Adverse Experience Reporting System (DAERS), an internet-based reporting system, must be used for expedited AE reporting to DAIDS. In the event of system outages or technical difficulties, expedited AEs may be submitted via the DAIDS EAE Form. For questions about DAERS, please contact DAIDS-ES at [contact]. Site queries may also be sent from within the DAERS application itself.

Where DAERS has not been implemented, sites will submit expedited AEs by documenting the information on the current DAIDS EAE Form. This form is available on the RSC website: <http://rsc.tech-res.com/safetyandpharmacovigilance/>. For questions about expedited reporting, please contact DAIDS RSC ([contact]).

7.3.2 EAE Reporting Requirements for this Study

- EAEs will be reported for women and infants enrolled in this study.
- The SAE Reporting Category, as defined in Version 2.0 of the DAIDS EAE Manual, will be used for this study.
- The study agents for which expedited reporting is required are: rifapentine and isoniazid. Open-label pyridoxine (vitamin B₆) and prenatal multivitamins are not to be considered for EAE reporting.

7.3.3 Grading Severity of Events

Severity and laboratory tests will be graded per the DAIDS Table for Grading Adult and Pediatric Adverse Events, Version 2.0 (dated November 2014 available on the RSC website (<http://rsc.tech-res.com/safetyandpharmacovigilance/>), except for complications during pregnancy. Complications during pregnancy will be graded per the Complications of Pregnancy Section of the Female Genital Grading Table for Use in Microbicide Studies (Version 1.0, dated November 2007) found on the DAIDS RSC website (<http://rsc.tech-res.com/safetyandpharmacovigilance/gradingtables.aspx>).

For any serious or expedited AEs (SAEs/EAEs) that are continuing at a participant's study exit visit, the IoR/designee must establish a clinically appropriate follow-up plan for the AE, including referrals to local standard of care. The same approach must be taken for any AEs that are found to have increased in severity at the time of the study exit visit or continue requiring re-assessments beyond the study exit visit.

Serious adverse events (SAEs) will be defined by the Manual for Expedited Reporting of Adverse Events to DAIDS (Version 2.0, January 2010), as AEs occurring at any dose that:

- Results in death
- Is life-threatening
- Requires inpatient hospitalization or prolongation of existing hospitalization
- Results in persistent or significant disability/incapacity
- Is a congenital anomaly/birth defect
- Is an important medical event that may not result in death, be immediately life-threatening, or require hospitalization but may jeopardize the participant or require intervention to prevent one of the outcomes listed in the definition above

7.3.4 Expedited AE Reporting Period

- The expedited AE reporting period for this study begins once the participant is enrolled and continues through and including the participant's final study visit (Mother or Infant Study Exit).
- After the protocol-defined AE reporting period, unless otherwise noted, only suspected unexpected serious adverse reactions (SUSARs) as defined in Version 2.0 of the EAE Manual will be reported to DAIDS if the study staff become aware of the events on a passive basis (from publicly available information).

8 PARTICIPANT MANAGEMENT – MOTHERS AND INFANTS

Guidelines for clinical management and temporary hold/permanent discontinuation of the study drug regimen are outlined in this section. In general, the IoR/designee has the discretion to hold study drug regimen temporarily at any time if s/he feels that continued use would be harmful to the woman or interfere with treatment deemed clinically necessary, and s/he should notify the Core Team in such cases. Unless otherwise specified below, the IoR/designee should immediately consult the Core Team for further guidance on resuming study drug regimen, continuing the hold temporarily, or progressing to permanent discontinuation of study drug regimen. The IoR/designee will document all temporary study drug regimen holds and permanent discontinuations on applicable CRFs. When indicated, sites should notify the Core Team within 48 hours. Unless otherwise specified, study drug regimen refers to RPT, INH, and pyridoxine.

8.1 Management of Adverse Events

Management of adverse events will be according to the best clinical practice and the judgment of the site investigator. Enrolled infants of women participating in IMPAACT 2001 are not actively provided with the study drug regimen but may be exposed in utero or through breastfeeding. Infant management is the responsibility of the clinical care provider at the site. AEs involving these infants should be reported according to requirements in Section 7 as well as to the local Institutional Review Board/Ethics Committee according to prevailing local law and Good Clinical Practices. All protocol-specific reportable events and SAEs will be recorded on CRFs as per Section 7.2. Unless otherwise specified, participants will remain on-study for the duration of the scheduled follow-up visits.

All adverse events identified in infants in this study will be source documented consistent with the policies and procedures referenced in Section 11. Among other details, source documentation will include the severity of each event (graded as described in Section 7.3.3) and its relationship to study product, assessed by the site clinician according to the following categories and definitions:

- *Definitely Related*: The adverse event and administration of the medication are related in time, and a direct association can be demonstrated.
- *Probably Related*: The adverse event and administration of the medication are reasonably related in time, and the adverse event is more likely explained by the medication than other causes.
- *Possibly Related*: The adverse event and administration of the medication are reasonably related in time, and the adverse event can be explained equally well by causes other than the medication.
- *Probably Not Related*: A potential relationship between the medication and the adverse event could exist (i.e., the possibility cannot be excluded), but the adverse event is most likely explained by causes other than the medication.
- *Not Related*: The adverse event is clearly explained by another cause not related to the medication.

Note: The above classification applies for AE documentation (source documentation and CRF completion) and management but does not apply for expedited adverse event (EAE) reporting. EAEs will be reported, per the DAIDS EAE Manual, as related or not related. Please see Section 7.3 for more information on EAE reporting.

8.1.1 Suspected TB Disease

- Hold study drug regimen (i.e., RPT, INH, and pyridoxine) for suspected TB disease
- Perform confirmatory test (specific test as determined by site IoR/designee)
- If active TB disease is confirmed, permanently discontinue study drug regimen and notify the Core Team. Women and infants diagnosed with active TB during the study will be referred to local care for active TB management and treatment, where (if available) they will have a sputum sample (or other appropriate sample if extrapulmonary TB) sent for drug susceptibility testing (DST) to ensure susceptibility to first-line regimens. .
- If active TB disease is not confirmed and the IoR/designee suspects active TB based on clinical judgment, the IoR/designee may choose to permanently discontinue study drug regimen, refer participant to local care for TB management, and notify the Core Team.
- If active TB disease is not confirmed, the IoR/designee may resume the woman on the study drug regimen.

8.1.2 Rifamycin hypersensitivity syndrome (RHS)

For women who develop signs or symptoms suggestive of RHS (e.g., fever, myalgia, rash, hypotension, clinical hepatitis):

- Hold study drug regimen
- Assess the women for RHS (see note below for definition) through clinical evaluation and laboratory testing, including comprehensive metabolic panel, CBC with manual differential, and other tests that, at the discretion of the site IoR/designee, are necessary to exclude likely alternative diagnoses (e.g., should symptoms suggest influenza, a nasopharyngeal aspirate for viral testing could be sent).
- If \geq Grade 2 AE or toxicity meets the case definition for RHS, permanently discontinue the study drug regimen and notify the Core Team.

In the event of treatment discontinuation, participants will remain on-study and continue to be followed through 24 weeks postpartum.

Note: RHS is defined as follows:

- Hypotension, urticaria, angioedema, acute bronchospasm, conjunctivitis, thrombocytopenia, or neutropenia that occurred in relation to study drug regimen; *or*
- More than four of the following that occurred in relation to study drug (one of which must be assessed as having been > Grade 2): weakness, fatigue, muscle pain, nausea, vomiting, headache, fever, aches, sweats, dizziness, shortness of breath, flushing, rash, itching, syncope, cough, palpitations, chills, or eosinophilia.
- A complete listing of RHS symptoms reported by the woman should be recorded on the appropriate CRFs.

8.1.3 Gastrointestinal

For Grade 2 AE with symptoms not present at the previous visit, or for nausea/vomiting and/or diarrhea \geq Grade 3:

- Hold study drug regimen until the symptoms have resolved. Antiemetic and antidiarrheal medication may be used at the site investigator's discretion

For nausea and vomiting occurring as a result of hepatitis (determined as unrelated to study drug regimen), hold study drug regimen until the symptoms return to baseline levels.

8.1.4 Cutaneous

For Grade 2 or 3 rash, or showing a significant increase over baseline, hold study drug regimen. When the AE resolves or returns to baseline, resume study drug regimen.

For Grade 4 cutaneous or Grade 4 mucocutaneous rash, hold study drug regimen. Study drug regimen may be interrupted and resumed at the discretion of the site investigator. If Grade 4 returns and is determined to be related, permanently discontinue study drug regimen.

8.1.5 Drug-Associated Fever

If \geq Grade 3, hold the study drug regimen. When the temperature returns to normal, resume the study drug regimen. If symptoms recur, permanently discontinue and notify Core Team.

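### Sections 8.1.4 and 8.1.5 direct resumption after rash or fever without referring to the RHS assessment in 8.1.2, and the protocol does not say which section governs

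*Protocol*

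**What the plan says.** Section 8.1.2 of the protocol opens "For women who develop signs or symptoms suggestive of RHS (e.g., fever, myalgia, rash, hypotension, clinical hepatitis". Its first step is "Hold study drug regimen", and its second is "Assess the women for RHS (see note below for definition) through clinical evaluation and laboratory testing", which includes a metabolic panel and a blood count with manual differential. No minimum grade applies to either step. If an event of at least "Grade 2 AE or toxicity meets the case definition for RHS, permanently discontinue the study drug regimen".

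The RHS definition in the note to 8.1.2 has two limbs. The first is any one of "Hypotension, urticaria, angioedema, acute bronchospasm, conjunctivitis, thrombocytopenia, or neutropenia that occurred in relation to study drug regimen". The second is "More than four of the following that occurred in relation to study drug", from a list that includes fever, rash and eosinophilia, with at least one item above Grade 2.

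Section 8.1.5, on drug-associated fever, says that at or above "Grade 3, hold the study drug regimen. When the temperature returns to normal, resume the study drug regimen". Permanent discontinuation follows only if symptoms come back.

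Section 8.1.4 says "For Grade 2 or 3 rash, or showing a significant increase over baseline, hold study drug regimen", and directs resumption once the event resolves or is back to baseline.

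Section 8.1.12 lets a woman with a Grade 1 or 2 event not covered elsewhere stay on drug at the investigator's discretion.

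**The concern.** Fever and rash are named triggers in 8.1.2 and are also the subjects of 8.1.5 and 8.1.4. The three sections do not lead to the same place. Through 8.1.2, the woman is held, assessed for RHS and, if the definition is met at Grade 2 or higher, stopped for good. Through 8.1.5 or 8.1.4, she is held (for fever, only from Grade 3) and restarted when the sign has gone, with no RHS assessment mentioned.

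Two things are at stake. The first is participant safety: a woman could be dosed again before anyone has looked for the other features of the syndrome. Section 13.5 itself describes RHS as potentially dangerous if it is not recognised promptly. The second is measurement. Adverse events leading to permanent discontinuation are a primary maternal safety outcome (9.2.1.2) and a tolerability outcome (9.2.2.3), and section 8.2 takes its toxicity criterion from 8.1. If sites in several countries enter through different sections, part of the variation in these counts reflects how the protocol was read.

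**Working it through.** The point is one of wording, so no formula applies. The check sets the sections side by side and then looks for anything that links them.

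| Situation | Under 8.1.2 | Under the single-sign section |
|---|---|---|
| Fever, Grade 1–2 | Hold and assess, if judged suggestive of RHS | 8.1.5 silent; 8.1.12 would permit continuing |
| Fever, Grade 3 or above | Hold and assess; permanent stop if the definition is met | 8.1.5: hold, resume when temperature is normal, permanent stop only on recurrence |
| Rash, Grade 1 | Hold and assess, if judged suggestive of RHS | 8.1.4: hold only if significantly increased over baseline |
| Rash, Grade 2–3 | Hold and assess; permanent stop if the definition is met | 8.1.4: hold, resume on resolution or return to baseline |

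**Is there a link or a rule of precedence?** Neither 8.1.4 nor 8.1.5 refers to 8.1.2, and 8.1.2 does not refer to them. Section 13.5 sends women with any RHS symptom for evaluation, without a grade limit, but does not say how that relates to 8.1.4 or 8.1.5. The authors do write such links elsewhere: 8.1.7 sends a participant who becomes symptomatic to the guidance on symptomatic hepatitis.

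**Does the opening of Section 8 close the gap?** It lets the investigator hold at any time, and makes consultation with the Core Team the default before resuming. That default gives way where a later section specifies otherwise. Sections 8.1.4 and 8.1.5 do specify resumption, so the default can be read as displaced. Section 8.1.5 brings in the Core Team only after recurrence.

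**Would the missed work-up matter?** Fever alone cannot meet the RHS definition. A Grade 3 fever does, however, supply the above-Grade-2 element of the second limb, and four further listed symptoms would complete it (one plus four is five, which is more than four). Neutropenia related to study drug meets the first limb alone, and eosinophilia counts towards the second. Routine blood counts on drug are every four weeks (6.3), and the components recorded are white count, hemoglobin and platelets (6.8.1), without a differential. The work-up in 8.1.2 is therefore the step most likely to find these features at the time of the event.

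**Can the effect be sized?** No. The documents give no rate of drug-associated fever by grade, no rate of rash by grade, and no indication of how often a site would choose one section over another.

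**The case against.** The best reply is that the sections do different jobs. The trigger in 8.1.2 is a clinical judgement that the picture suggests RHS, and fever is only an example. Section 8.1.5 concerns a fever already attributed to drug. Nothing in it switches off 8.1.2, and a site can follow both. Section 8.1.2 also has no restart rule for the woman in whom RHS is excluded, and 8.1.4 and 8.1.5 can be read as supplying it. This is a sensible reading. But the protocol does not state it, and it names fever and rash themselves as triggers, so a literal reader of 8.1.5 or 8.1.4 is not led to the assessment.

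Four stronger readings are tempting, and the documents do not support them.

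- **A reader might infer that a low-grade fever meets opposite instructions.** Below Grade 3, section 8.1.5 says nothing. It does not order continuation, 8.1.12 only permits it, and the investigator may hold at any time.
- **A reader might infer that Grade 2 urticaria is stopped for good under 8.1.2 but restarted under 8.1.4.** The RHS definition lists urticaria in its first limb and rash separately in its second. The protocol thus distinguishes the two, and 8.1.4 speaks only of rash.
- **A reader might infer that RHS is found only through 8.1.2.** All signs and symptoms on study drug are recorded (7.2), the Core Team reviews safety data about twice a month (7.1), and the protocol team settles attribution of events of Grade 3 or higher (9.6.2). RHS is also not itself an outcome in 9.2.
- **A reader might size the effect from Table 1.** Assuming 30 HIV-negative and 20 HIV-positive women, 30 × 0.046 + 20 × 0.01 = 1.58 cases of possible hypersensitivity. That mix is an assumption. The safety analysis takes every dosed woman, with up to 82 enrolled, and Table 1's category is not shown to match the RHS definition. Nor does the figure say how many cases would be handled under the wrong section.

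It is also fair to say that a brief hold may change no dose: doses are weekly with a two-day margin either way, and 12 doses may be spread over 16 weeks (5.1.1, 5.1.2).

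**Conclusion.** The point holds as a gap in how the sections fit together. A site following 8.1.4 or 8.1.5 alone can resume dosing without the RHS assessment in 8.1.2, and the protocol does not say which section governs when both apply. Holds and permanent discontinuations can therefore depend on the section chosen. This bears on participant safety and on the outcomes in 9.2.1.2 and 9.2.2.3.

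Its size cannot be estimated from the documents. The conclusion rests on the wording alone and needs no assumed fever rate or HIV mix. It does assume that some sites would apply the single-sign section without also turning to 8.1.2; the text allows this but does not require it. The point should be put right because it touches safety and is cheap to settle. It does not undermine the design or show that the safety results would be wrong.

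**What to change.** Reconcile 8.1.2 with 8.1.4, 8.1.5 and 8.1.12 by stating how they relate. The text should say:

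- whether the 8.1.2 assessment applies before dosing is resumed under 8.1.4 or 8.1.5;
- which section governs when a woman's fever or rash falls under both;
- whether 8.1.12 is meant to cover drug-associated fever below Grade 3.

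The clinical rule and any grade thresholds are for the sponsor's clinicians, and no view is offered here on what they should be.

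The cost is a few cross-references in a clarification memo or amendment and a note to sites. The cross-references themselves add no procedure beyond those 8.1.2 already requires.
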